7.10.2.3 Secondary endpoint#3

The secondary objective#3 is to measure health care utilization costs during the study period. The Health Economic Analysis Plan (HEAP) will be developed for this secondary endpoint and other additional analyses.

7.11 Safety Evaluation

Adverse events will be presented using the MedDRA coding and with the following summary tables and supporting data listing:

Table 28 – Adverse Event by Primary System Organ Class and Preferred Term – FAS

Table 29 – Adverse Event Seriousness and Relatedness– FAS

Table 30 – Individual Adverse Events for which Sponsor and Investigator disagreed – FAS

Listing2- Individual Adverse Events - FAS

Table 31 – Death Summary – FAS (if appropriate)

Listing 3- Death – FAS (if appropriate)

7.12 Changes to Planned Analysis

The analysis described in the CIP could differ from that presented in this SAP due to data availability. In case a lower rate of enrollment will occur or any other unexpected

issue which reduce the sample size or event rate a new strategy will be adopted to protect the derivation cohort and to allow at least the derivation of the score^{6,7} (see section 9.2 for details).

8 Validation Requirements

All collected data will be reviewed for completeness, correctness and consistency. In case of issues, queries will be sent to the investigator to complete, correct or comment the data. To ensure the quality of the results provided for the study in the form of tables, listings and figures, and the derived datasets the following processes are used:

- Statistical programming and analysis will be done by qualified programmer(s) and statistician(s) following applicable procedures and best practices.
- The derived datasets will be validated by a second programmer or statistician.
- The tables will be validated by a second programmer or statistician.
- Statistical results will be reviewed and confirmed by a second statistician.

The entire set of tables, listings, and figures (TLF) will be 100% checked for accuracy, completeness, and consistency prior to inclusion in the interim or final clinical study report. According to Medtronic SOPs the level II validation (the peer reviewer reviews the code; where appropriate, performs manual calculations or simple programming checks to verify the output) will be implemented for both Datasets and TLFs.

9 References

1. <http://www.strobe-statement.org/index.php?id=available-checklists>
2. Mary L. McHugh: Inter rater reliability: the kappa statistic (<https://www.ncbi.nlm.nih.gov/pmc/articles/PMC3900052/?report=reader>)
3. Frank e. Harrell, Multivariable prognostic models: issues in developing models, evaluating assumptions and adequacy and measuring and reducing errors, *Statistics in Medicine*, vol. 15,361-387 (1996)
4. Presentation of multivariate data for clinical use: The Framingham Study risk score functions, Lisa M. Sullivan, Joseph M. Massaro, Ralph B. D'Agostino Sr., *Tutorial in Biostatistics, Stat. Med* 2004
5. Ronen M., Smart respiratory monitoring: clinical development and validation of the IPI™ (Integrated Pulmonary Index) algorithm, *Journal of Clinical Monitoring and Computing*, pp 1-8 mar 2016

9.1 Measures for model validity

The measures calculated will be:

- The **concordance**: the c statistic. For binary outcomes, c is identical to the area under the receiver operating characteristic (ROC) curve; c varies between 0.5 and 1.0 for sensible models (the higher the better).

- The **calibration slope** is the regression coefficient b in a logistic model with the predictive score as the only covariate: $\text{logit}(\text{mortality}) = a + b * \text{predictive score}$. Well-calibrated models have a slope of 1, while models providing too extreme predictions have a slope less than 1.
- The **Brier score** (or average prediction error) is calculated as $\text{Sum}(y_i - p_i)^2/n$, where y_i denotes the observed outcome and p_i the prediction for subject i in the data set of n subjects.
- The **D statistic** is a scaled version of the model chi-square, which is a function of log-likelihood
- The **R²** as a measure of explained variation.

The table below summarize the three aspects to be checked for model validity:

Aspect	Measure	Characteristics
Calibration	Calibration plot	Visual impression of observed frequencies vs. predicted probabilities
	Slope	Estimate of extremeness of predicted probabilities
	Intercept	Estimate of systematically too high/low predicted probabilities
	E_{avg}	Average absolute difference between observed frequencies and predicted probabilities
	Hosmer-Lemeshow Statistic	Test for 'goodness-of-fit', i.e. deviance of grouped observed outcomes and predicted outcomes
Discrimination	Boxplot of predicted probabilities	Visual impression of spread in predicted probabilities; relies on adequate calibration
	c-statistic (ROC area)	Summary of quality over a range of threshold values
Clinical usefulness (threshold value required)	Accuracy	Percentage of patients correctly classified, given a certain threshold value
	Sensitivity	Percentage of patients with the outcome correctly classified as diseased
	Specificity	Percentage of patients without the outcome correctly classified as non-diseased
	Decrease in weighed false classifications	Model and reference policy are compared by weighing patients falsely classified as diseased and non-diseased according to relative severity

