13.3. Primary Endpoint

At the end of data collection all subjects enrolled will be randomly assigned to the derivation set and the validation set at a ratio of 2 to 1. According to the outcome of the planned RD event rate monitoring, there could be the possibility to use the overall population as the derivation cohort. The validation sets will be performed using a bootstrapping method. A detailed description of the bootstrap method will be

Version 3.0, 29 Nov 2016

PRODIGY CIP

reported in the Statistical Analysis Plan (SAP). Bivariate odds ratios (ORs) and 95% confidence intervals (95% CIs) will be estimated. The possibility of collinearity between categorical variables will be also tested. The logistic regression model will be performed using a backward stepwise selection procedure in which the presence of event will be the dependent variable. Independent predictors will be entered into the model if a significant association, defined as $p \le 0.05$, will be identified from bivariate analysis and, to avoid over-fitted and unstable model the correlation coefficient between them should be less than 0.25.

The predictive risk score for RD will be calculated by multiplying each b coefficient (from the multivariate model by 10 and rounding to the nearest integer. The integers will then be added together to produce an overall RD risk score for each subject. The resulting continuous distribution of total risk scores across all subjects in the derivation set will be then stratified into 3 categories of points that grouped subjects according to the level of risk (low, medium and high risks). Model prediction performance will be assessed using calibration (the agreement between predicted and observed outcome) and discrimination (the ability to separate subjects with and without the outcome) and the R2 will be reported as an overall measure for discrimination and calibration. The Sensitivity and Specificity and the receiver-operating characteristic (ROC) curves will be used to visualize the overall accuracy of the model. The discriminatory performance of the model will be validated by comparing the ROC curve analysis in the derivation set with that in the validation set.

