7.10.1.1 Deriving the model

Note for Programmer: The analysis for the primary objective will be performed on a Dataset with one row per patient with RD episode as validated by CEC as the dependent variable (at least one RD) and baseline predictors as independent variables. Potential predictors will be reported on continuous scale or grouped into categories.

The logistic model will be used for bivariate e multivariate odds ratios (ORs) and 95% confidence intervals (95% CIs) will be estimated for each potential predictor. The following steps will be followed to derive the score for each predictor according to categories⁴:

- Determine categories for each risk factors (the most will be 0/1)
- Determine reference class for each risk factor (for dummy the reference category is 0)
- Calculate mid-values to represent categories
- Determine multiplier β
- Determine point score for each risk factor category

If **Data Split** approach:

- Repeat multivariate model on the validation set
- Calculate performance measures
- The "Optimism" is the difference between the performance measures from validation and derivation set

If **Bootstrapping** approach:

- 500 bootstrapped replications of the multivariate model

- Calculate performance measures bootstrapped
- The difference between the bootstrapped performance and the model performance will be averaged to obtain an estimation of the “optimism” of the model. The optimism will be used to validate the model.

Table 25 - RD Risk Score Derivation identified by logistic – MFAS

Predictors	Bivariate analysis OR (95% CI) (N=XXXX)	Multivariate analysis OR (95% CI) (N=XXXX)	Coefficient	Adjusted Coefficient	Risk score point
Char#1	x.xx (x.xx- x.xx)	x.xx (x.xx- x.xx)	x.xxx	x.xx (x.xx- x.xx)	xx
Char#2	x.xx (x.xx- x.xx)	x.xx (x.xx- x.xx)	x.xxx	x.xx (x.xx- x.xx)	xx
...					
Char#N	x.xx (x.xx- x.xx)	x.xx (x.xx- x.xx)	x.xxx	x.xx (x.xx- x.xx)	xx

The collinearity between categorical variables will be also tested by means the Cramer V test for nominal variables and Kendal’s tau-b for ordinal variables. The multivariate logistic regression model will be performed using a stepwise selection procedure in which the presence of event will be the dependent variable. Independent predictors will be entered in to the model if a significant association, defined as $p \leq 0.05$, will be identified from bivariate analysis and, to avoid over-fitted and unstable model the correlation coefficient between them should be less than 0.25.

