The predictive risk score for RD, based on the best model selected from analysis above, will be calculated by multiplying each β coefficient taken from the final multivariate model by 10 and rounding to the nearest integer. The integers will then be added together to produce an overall RD risk score for each patient. The resulting continuous distribution of total risk scores across all patients in the derivation set will be then stratified into categories of points (depending on the total sample the quintiles or tertiles or optimal cutoff points) that grouped patients according to the level of risk.

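### SAP 9.1 defines the calibration slope with mortality instead of RD as outcome and leaves its covariate undefined; if the integer score is meant, the target of 1 does not apply

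*SAP*

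**What the plan says.** SAP 9.1 lists the measures of model validity. The calibration slope is the "regression coefficient b in a logistic model with the predictive score as the only covariate". The equation printed beside it is logit(mortality) = a + b × predictive score. The reading rule follows: "Well-calibrated models have a slope of 1, while models providing too extreme predictions have a slope less than 1". The table in the same section lists a slope and an intercept among the calibration measures.

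The model itself is built on a different outcome. SAP 7.10.1.1 specifies a "Dataset with one row per patient with RD episode as validated by CEC as the dependent variable", and SAP 7.10.1 names the RD episode as the primary endpoint. Elsewhere in the SAP, mortality appears only in secondary endpoint 1 (7.10.2.1) and as deaths in the safety outputs (7.11).

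The one score the SAP constructs is in 7.10.1.1: "The predictive risk score for RD, based on the best model selected from analysis above", obtained by "multiplying each β coefficient taken from the final multivariate model by 10 and rounding to the nearest integer". Then: "The integers will then be added together to produce an overall RD risk score for each patient". Protocol 13.3 has the same scaling ("by 10 and rounding to the nearest integer"). Neither document divides the score by 10 or converts it back to log-odds for the slope.

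**The concern.** A calibration slope compares a model's predicted log-odds with the observed outcome that the model predicts. Section 9.1 departs from this in one way that is certain and in one that depends on the reading.

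- **Outcome.** The equation regresses death on an RD score. No objective of the study is to predict death with this tool.
- **Covariate.** The target of 1 presupposes a covariate on the log-odds scale. If the predictive score is the integer score of 7.10.1.1, the covariate is about ten times too large and the target is wrong by the same factor.

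Validation is half of the primary objective, and calibration is one of the performance properties named in Protocol 13.3 and SAP 7.10.1.2. Within 9.1, the slope is the measure assigned to extremeness of predictions, the usual sign of overfitting. Overfitting is a live issue in a design with about 10 events per variable, bivariate screening and stepwise selection.

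**Working it through.** **Inputs from the documents.** Slope equation, outcome and target of 1: SAP 9.1. Modelled outcome (at least one CEC-validated RD per patient) and score scale: SAP 7.10.1.1. RD incidence of 12%: SAP 6.

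**Assumptions.** The documents give no coefficients, so three sets were drawn for 12 binary predictors, in the ranges 0.09–0.51, 0.18–1.02 and 0.3–1.7. A death rate of 1% was assumed. The true coefficients were used throughout, so the RD model is perfectly calibrated by construction. Each set had 400,000 simulated subjects.

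**1. The plan's target of 1.** Let LP = β₀ + Σβⱼxⱼ. Under perfect calibration logit P(RD) = LP = 0 + 1 × LP, so a = 0 and b = 1. The target is reproduced with RD as outcome and LP as covariate.

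**2. The integer score as covariate, RD as outcome.** S = Σ round(10βⱼ)xⱼ ≈ 10(LP − β₀), so LP ≈ β₀ + S/10. Then logit P(RD) ≈ β₀ + 0.1 × S. Perfect calibration gives b ≈ 0.1, and the intercept is β₀ rather than 0.

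| Coefficient range | RD on LP | RD on S | RD on S/10 |
|---|---|---|---|
| 0.09–0.51 | 0.992 | 0.0987 | 0.987 |
| 0.18–1.02 | 0.989 | 0.0994 | 0.994 |
| 0.3–1.7 | 1.002 | 0.1005 | 1.005 |

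In 300 simulated validation sets of 500 (coefficients 0.3–1.0), the slope on S averaged 0.102, with 95% of values between 0.07 and 0.13. A slope of 1 on S would need an odds ratio of exp(1) = 2.72 per point, or exp(10) ≈ 22,000 per ten points, which is one unit of LP.

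**3. Miscalibrated scores.** If the score is built from coefficients c times the true ones, b ≈ 1/(10c).

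- Too extreme, c = 1.5: 1/15 = 0.067.
- Correct, c = 1: 1/10 = 0.100.
- Not extreme enough, c = 0.7: 1/7 = 0.143.

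A separate simulation with six binary predictors gave 0.065, 0.099 and 0.140. Against a target of 1, all three read as too extreme, including the one that errs the other way. Against 0.1 they are ordered correctly.

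**4. Mortality as outcome, as printed.** Suppose the log-odds of death rise by f per unit of LP. The slope is then about f on LP and f/10 on S. For f = 0, 0.5 and 1, the simulated slopes on S were about 0, 0.05 and 0.10 in all three coefficient sets, and those on LP about 0, 0.5 and 1. The RD model was perfectly calibrated in every case. The slope therefore reports how death relates to the RD predictors, and there is no fixed value that signifies good RD calibration.

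**The case against.** The strongest objection concerns the scale. Section 9.1 says predictive score, whereas 7.10.1.1 says predictive risk score. The table in 9.1 describes the slope and intercept in terms of predicted probabilities that are too extreme, or systematically too high or too low. Those descriptions fit a log-odds covariate, for which 1 is correct. This stands: the linear predictor may well have been meant. But 9.1 does not say so, and the integer sum is the only score a programmer will find defined.

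The objection on consequence also stands in large part. SAP 7.10.1.2 and Protocol 13.3 validate discrimination by comparing ROC curves. SAP 9.2 spells out bootstrap optimism for R² only. No acceptance threshold is attached to the slope, and none of the outputs listed in 7.10.1.2 names it. Figure 4 there plots observed frequency against predicted probability, and E_avg, the Hosmer-Lemeshow statistic and the Brier score do not use the faulty equation.

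Misuse is also less likely than the text alone suggests. The analysis dataset has RD as dependent variable, and SAP 8 requires a second statistician to confirm results. That lowers the risk but does not correct the text, and no reading of 9.1 makes mortality the right outcome.

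A reader might infer that the plan will condemn a well-calibrated tool, or that calibration will go unassessed. The documents support neither: the first needs the integer-score reading plus a decision rule that does not exist, and the second overlooks the other calibration measures. Nor does the integer scale destroy the information in the slope. The values in step 3 are distinct, and a known factor of 10 restores them.

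**Conclusion.** The outcome in the SAP 9.1 slope equation is wrong as written: it should be CEC-adjudicated RD. With mortality, the slope does not measure calibration of the RD tool.

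The scale problem is conditional. If the covariate is the integer score and the outcome is RD, perfect calibration gives about 0.1, and comparison with 1 would misread it by a factor of ten. If the covariate is the linear predictor, 1 is correct and the SAP need only say so. It would be a mistake to quote 0.1 as the target of the printed equation, because that figure holds only once RD has replaced mortality.

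The value of 0.1 follows from the algebra for any coefficients, up to rounding of the points. The simulated figures rest on assumed coefficients and, for step 4, an assumed 1% death rate. The effect is confined to the slope and the intercept of the same equation. This should be fixed before the slope is computed, but it does not threaten the score derivation or the other validation measures.

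**What to change.** In SAP 9.1:

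- Replace mortality with CEC-adjudicated RD (at least one per patient).
- Define the covariate as the linear predictor, with intercept and coefficients frozen from the derivation model. For the integer score, use derivation intercept + score/10.
- Under the bootstrap route, apply each bootstrap model's linear predictor to the original sample.
- Apply the slope target of 1 and the intercept target of 0 on that scale only.

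The freezing needs to be explicit. SAP 7.10.1.1 repeats the multivariable model on the validation set under the data-split route, and a refitted model's own linear predictor has slope 1 and intercept 0 in that set by construction.

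The cost is one line of SAP wording. No new data are needed.

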9.2 Bootstrap Method

Bootstrapping will be considered as an alternative method of internal validation that involves taking a large number of samples with replacement from the original sample. Bootstrapping provides unbiased estimates of predictive accuracy and it has the advantage to use the entire dataset for model development. A total of 500 bootstrapped replications will be performed. For each replication the univariate and multivariate models will be run. According to results, the R^2 as the average of R^2 from each replication will be calculated. The difference between average bootstrapped R^2 and model R^2 will represent the "optimism" of the model compared to the bootstrapped models. The optimism will consider as the validation of the model.

9.3 Detection Tool

The Detection Tool analyzes each patient's monitoring using an algorithm based on the device episodes thresholds as stated in the primary endpoint. The Detection Tool provides for each patient multiple Episodes. Since there could be multiple episodes in a short time period around each Episode, the Detection Tool is set to aggregate episodes with at most 30 minutes time difference between them in one file. In addition the episodes file consists of time window of 30 min before and after the first and last episode.

9.4 Priority List

The CEC will stop the adjudications at the first RD for each patient, while they will adjudicate all Clinical Events. In order to optimize CEC time the following priority list will be used to prioritize some Episode-File to be review first:

Priority 1: all clinical events with/without any episode from device data. In case multiple Clinical events per patient the CEC will review them using the time of occurrence, from first clinical event to the last.

Priority 2: Multiple episodes involving at least two parameters among SpO₂, EtCO₂, RR and Apnea. In case of multiple Episode-Files with this priority the CEC will review first the Episode-Files with the higher number of Episodes within the Episode-Files.

Priority 3: Multiple Episodes of the same parameter. In case of multiple Episode-Files with this priority the CEC will review using this order: SpO₂, EtCO₂, RR and Apnea

Priority 4: Any overnight Episodes of the same parameter. In case of multiple Episode-Files with this priority the CEC will review using this order: SpO₂, EtCO₂, RR and Apnea

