9.1. Schedule of Events

Data will be collected for Screening, Enrollment Visit, the Capnographic Monitoring Period, 1 month Follow Up Visit, and Study Exit. Additional data will be collected for Adverse Events, Device Deficiencies, and Protocol Deviations.

Data collection requirements are summarized in Table 2. The study site personnel must report all study specific Adverse Events and changes in status of these Adverse Events from time of enrollment until a subject exits the study.

Table 2. Data Collection Requirements

PRODIGY CIP

056-F275, Clinical Investigation Plan Template, Version 2.0

Data	Screening Evaluation	Enrollment	Capnography Monitoring	1 Month Follow up	Study Exit
Informed Consent	x				
Inclusion/Exclusion Criteria Evaluation	x				
Medical History		x			
Demographic & Physical Exam		x			
Vital Signs		x	x		
Supplemental Oxygen Use		x	x		
Surgery Information		x			
Care Pathway			x		
Monitoring Duration			x		
Medications		x	x		
Adverse Events		x	x	x	x
Device Memory Data			x		
Product Information			x		
Device Deficiencies			x		
Protocol Deviations	x	x	x	x	x
Healthcare Resource Utilization				x	x

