13.2. Data Analysis

A detailed description of the statistical methods will be contained in the Statistical Analysis Plan (SAP). Any change to the data analysis methods described in this section and/or the SAP will require an amendment only if it changes a principal feature of the study description. Any other changes to the data analysis methods will be described and justified in the Final Report or publication.

Based on the clinical practice in the opioid used and number of subjects enrolled per centre/country, an investigation of centre/country effect will be investigated including an independent variable for centres/country in the model as well as summary statistics if needed.

The choice of the imputation method for missing data will depend on the pattern of the missingdata and the type of the imputed variable.

The primary analysis will be performed on all subjects enrolled in the study and monitored with the Capnostream monitor and include all clinical outcomes that occur within the monitoring period(s) as for study design.

It is anticipated that SAS (SAS Institute Inc., Cary, NC, USA) will be used to perform all statistical analyses. Statistical tests will be based on a two-sided significance level of 0.05, and interaction effects will be evaluated at a significance level of 0.10. No adjustments for multiple comparisons will be performed. Additional exploratory analyses will be conducted as deemed appropriate.

The statistics above will be calculated by means of a GEE model as appropriate in order to take into account multiple events per subject and they will be reported together with the interval confidence (IC).

All assumptions for regression models will be assessed by viewing plots of the residual values.

Descriptive statistics will be used to summarize subject characteristics. This will include mean, standard deviation, median, minimum, and maximum for continuous variables, and counts and percentages for categorical variables. To compare subjects with and without the outcome, all categorical variables will be analyzed with the Chi-square test or the Fisher exact test or Cochran-Mantel-Haenszel test for trend for ordinal variables with 3 or more categories, as appropriate. Continuous variable parameter comparisons will be performed using t-test or Wilcoxon test according to the normal or non-normal distribution.

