7.10.1 Primary endpoint

The primary endpoint that will be used to derive and validate the risk score assessment is the RD episode, defined as a clinical diagnosis made after reviewing monitoring data in conjunction with the clinical data and consistent with accepted pathophysiologic mechanisms. The primary endpoint used to derive the score will be the occurrence of RD episodes captured by continuous capnography and pulse oximetry measurements recorded on the Capnostream device memory data in conjunction with the clinical data as reported by the Investigators. RD determination will be validated by an independent Clinical Event Committee (CEC). The CEC will use both clinical data and monitor parameters specified below as a guideline; if determination of an RD episode is clinically appropriate but outside of the guidelines a rationale will be provided. Data suggestive of an RD episode include any of the following:

RR ≤ 5 breaths for ≥ 3 minutes
SpO2 ≤ 85% for ≥ 3 minutes

etCO ₂ ≤ 15 or ≥ 60 mmHg for ≥ 3 minutes
Apnea episode lasting > 30 seconds
Any respiratory Opioid-Related Adverse Event (rORADE)

The assessment of RD episodes will be made by the analysis of the Capnostream and clinical data for each patient. For each patient all potential RD episodes will be derived using the Detection Tool (see section 9.3) and will be submitted to the CEC according to a Priority List (see section 9.4) in order to adjudicate the potential RD episodes starting from RD episodes most likely to be RD. The CEC adjudication will stop the adjudication at the first RD occurring per patient (all details on CEC process are reported in the CEC Charter version 3.0).

All potential RD episodes in the study will be always rated by 3 coders (see detail in the Clinical Events Committee Charter Template, Version 3.0).

Patients of the MFAS will be randomly assigned (2:1) into respectively the derivation and the validation cohort. In case of low enrollment rate or low episode rate or according the outcome of a preliminary assessment of the events per variable or unbalanced enrollment per site/country the MFAS could not be randomized but used for model building and the bootstrap method, deriving 500 computer-generated samples by random selection with replacement for model validation³ (see section 9.2 for details).

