7.10.2.2 Secondary endpoint#2

The secondary objective#2 will characterize the predictive values of etCO₂, RR, SpO₂ and the IPI⁵ in predicting rORADE. To evaluate the predictive values of the Capnostream monitoring parameters for rORADE, the Sensitivity, Specificity, PPV and NPV will be calculated. rORADE events will be considered the Gold standard and the CS20p monitoring parameters as the measurement to be tested. The population used for this endpoint is PRDPS adjudicated as RD. All Clinical Events occurring during not monitored period will be reported but excluded from the table below. For each RD adjudicated by the CEC, the Capnostream monitoring will be checked if any of the parameter meets at least once the thresholds (RR \leq 6 breaths for \geq 3 minutes, SpO₂ \leq 85% for \geq 3 minutes, EtCO₂ \geq 60 mmHg for \geq 3 minutes or IPI < 3,4,5,6). The table below shows the distribution of the true and false positive and negative for each monitored parameter:

Test		Gold Standard		
Monitoring Parameter		ORADEs/RDs		
RR ≤ 5 breaths for ≥ 3 minutes		YES	NO	Tot
	YES	TP	FP	TP+FP
	NO	FN	TN	FN+TN
	Tot	TP+FN	FP+TN	N
Monitoring Parameter		ORADEs/RDs		
SpO2 ≤ 85% for ≥ 3 minutes		YES	NO	Tot
	YES	TP	FP	TP+FP
	NO	FN	TN	FN+TN
	Tot	TP+FN	FP+TN	N
Monitoring Parameter		ORADEs/RDs		
etCO2 ≤ 15 or ≥ 60 mmHg for ≥ 3 minutes		YES	NO	Tot
	YES	TP	FP	TP+FP
	NO	FN	TN	FN+TN
	Tot	TP+FN	FP+TN	N
Monitoring Parameter		ORADEs/RDs		
IPI <3		YES	NO	Tot
	YES	TP	FP	TP+FP
	NO	FN	TN	FN+TN
	Tot	TP+FN	FP+TN	N
IPI <4		YES	NO	Tot
	YES	TP	FP	TP+FP
	NO	FN	TN	FN+TN
	Tot	TP+FN	FP+TN	N
IPI <5		YES	NO	Tot
	YES	TP	FP	TP+FP
	NO	FN	TN	FN+TN
	Tot	TP+FN	FP+TN	N
IPI <6		YES	NO	Tot
	YES	TP	FP	TP+FP
	NO	FN	TN	FN+TN
	Tot	TP+FN	FP+TN	N
Monitoring Parameter		ORADEs/RDs		
Any Monitoring Parameter RR ≤ 6 breaths for ≥ 3 min or SpO2 ≤ 85% for ≥ 3 min or EtCO2 ≥ 60 mmHg for ≥ 3 min or IPI < 3,4,5,6		YES	NO	Tot
	YES	TP	FP	TP+FP
	NO	FN	TN	FN+TN
	Tot	TP+FN	FP+TN	N

Where:

- N will be all RDs adjudicated by the CEC.
- TP= true positive are all rORADEs and parameter over/below the threshold.
- FN= false negative are all rORADEs but no parameter over/below the threshold.
- FP= false positive are all no rORADE but parameter over/below the threshold.
- TN=true negative are all no ORADEs and no parameter over/below the threshold.

Measure of the accuracy will be:

- Sensitivity: $\{TP/(TP+FN)\}$,
- Specificity: $\{TN/(FP+TN)\}$,
- Positive predictive value: $\{TP/(TP+FP)\}$,

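### SAP 9.4 reviews clinical events first and stops at the first RD without the monitoring-period limit of Protocol 13.2, so some patients' primary outcome may be miscoded or undetermined

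*SAP*

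**What the plan says.** Protocol 13.2 says the primary analysis will "include all clinical outcomes that occur within the monitoring period(s) as for study design". Protocol 9.6 caps monitoring at 48 hours and allows it to be split into periods with gaps. Clinical events are followed for much longer: Protocol 9.1 has sites report adverse events and "changes in status of these Adverse Events from time of enrollment until a subject exits the study", and the follow-up contact is at about 30 days.

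The SAP sets the order of adjudication in 9.4. First comes "Priority 1: all clinical events with/without any episode from device data". Within that tier, "In case multiple Clinical events per patient the CEC will review them using the time of occurrence, from first clinical event to the last". Device Episode-Files are Priorities 2 to 4. The stop rule appears twice: in 9.4 ("The CEC will stop the adjudications at the first RD for each patient, while they will adjudicate all Clinical Events") and in 7.10.1 ("The CEC adjudication will stop the adjudication at the first RD occurring per patient").

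SAP 7.10.1.1 builds the primary dataset with one row per patient and "RD episode as validated by CEC as the dependent variable (at least one RD"; the parenthesis closes there, with no time limit. Events outside monitoring are addressed once, for secondary endpoint #2: "All Clinical Events occurring during not monitored period will be reported but excluded from the table below".

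**The concern.** The protocol and the SAP do not draw the same line around the primary outcome. Under the SAP's order, a clinical event in unmonitored time is reviewed before any device episode. If the CEC confirms it as RD, review of that patient's Episode-Files ends.

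Two routes follow, and neither is clean. If the SAP is followed literally, the patient is a case because of an event that Protocol 13.2 leaves out. If Protocol 13.2 is applied when the dataset is built, the out-of-window event is removed, but nobody has established whether the patient had RD during monitoring. SAP 7.4 does not impute the outcome, so such a patient could default to non-case.

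At stake is the dependent variable of the risk score. It could mix RD during ward monitoring with opioid-related respiratory events at other times, or miss in-window cases.

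**Working it through.** **Is the limit anywhere in the SAP's primary-outcome text?**

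- Protocol 13.2: the primary analysis is tied to the monitoring period(s).
- SAP 7.10.1: any respiratory opioid-related adverse event is on the list pointing to RD; no window.
- SAP 7.10.1.1: at least one CEC-validated RD; no window.
- SAP 9.4: all clinical events, with or without device data, in time order; no window.
- SAP 7.10.2.2: unmonitored-time events excluded, for endpoint #2 only.

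The SAP foresees such events and handles them for one secondary endpoint, but not for the primary outcome.

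**Can such events arise by design?** Yes. Adverse-event collection runs to study exit. Surgical patients consent before the operation (Protocol 9.3), so collection can start before ward monitoring. Monitoring may have gaps. The modified full analysis set (MFAS) keeps patients who never start monitoring (SAP 7.1.3).

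**When is the coded outcome wrong?** Consider a patient whose confirmed clinical RDs all fall outside monitoring.

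| True in-window status | SAP taken literally | Out-of-window event dropped, files unreviewed |
|---|---|---|
| RD present | coded 1, correct | coded 0, wrong |
| RD absent | coded 1, wrong | coded 0, correct |

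If x patients are in this position and a fraction p of them had in-window RD, then (1 − p)x are miscoded on the first route and px on the second. The documents do not give p.

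**How large could x be?** First, the plan's own figures (Protocol 13.1 to 13.1.2, SAP 6):

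- Derivation cohort: 10 × 12 / 0.12 = 1000.
- Both cohorts: 1000 × 3/2 = 1500; with 10% added, 1500 × 1.10 = 1650. These match the plan.
- Planned RD subjects: 0.12 × 1500 = 180.

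Then an illustration: x = 1500 × r × s, where r is the 0.3% to 3.4% intervention-based RD rate in Protocol 4.1 (post-surgical patients) and s is the share of patients with clinical RD whose confirmed events all fall outside monitoring. The documents give no s; the values below are assumptions.

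| s (assumed) | r = 0.3% | r = 3.4% |
|---|---|---|
| 10% | 0.45 (0.25% of 180) | 5.1 (2.8%) |
| 25% | 1.1 (0.6%) | 12.75 (7.1%) |
| 50% | 2.25 (1.25%) | 25.5 (14.2%) |

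The 180 is only a yardstick, since the 12% rate was built from device thresholds.

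**Effect on events per variable.** Suppose all such patients were among the 120 planned derivation cases and were dropped. At r = 0.3%, s = 10% the loss is 1000 × 0.003 × 0.10 = 0.3, giving 119.7 / 12 = 9.975. At r = 3.4%, s = 50% the loss is 17, giving 103 / 12 = 8.6. The plan is sized at 10.

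**The case against.** The strongest reply is that the window is already in the plan. Protocol 13.2 states it, and the SAP says it is based on that protocol. Both documents define RD as a diagnosis made from monitoring data together with clinical data, and a respiratory opioid-related event is a guideline item for the CEC, not automatic RD. Protocol 12.1 also gives the CEC separate tasks, so adjudicating every clinical event may serve only to classify adverse events. SAP 7.10.1 leaves process details to the CEC Charter, which is not among the documents and may hold a window.

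Much of this stands. A reader might infer that the SAP overrides the protocol, or that any late event becomes a case; the text shows only an omission. But Priority 1 expressly covers events without device data, and the endpoint #2 exclusion shows that unmonitored-time events were in view, so the list cannot safely be read as limited to monitored events. If the charter has a window, the SAP still needs a matching sentence, because the SAP defines the dependent variable.

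Three further inferences fail:

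- That every exposed patient is miscoded. A patient with in-window RD is coded 1 correctly under the SAP's literal rule.
- That the in-window outcome is lost. Protocol 15.2.2 has device memory data exported for each subject and transferred to the sponsor, so unreviewed files can still go to the CEC.
- That 30 days against 48 hours means 15 times the exposure to risk. That ratio (30/2) is calendar time, while the study concerns patients on parenteral opioids on the ward.

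**Conclusion.** The mismatch is real and touches the primary outcome. The SAP's order and stop rule, followed as written, can code an out-of-window event as the primary outcome or, once Protocol 13.2 is applied, leave in-window status undetermined.

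The coded value is wrong only in two situations. One is that all confirmed clinical RDs lie outside monitoring and there is no in-window RD. The other is that out-of-window events are dropped and an in-window RD went unreviewed.

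The number of exposed patients cannot be derived from the documents. Under the assumed shares of 10% to 50% it runs from under 1% to about 14% of planned RD subjects. The upper figure combines the top of a post-surgical rate with an assumed one-half share in a mixed surgical and non-surgical cohort, so it is not an estimate. The effect may be very small, and the unseen charter may already deal with part of it. This is a should-fix point, not grounds for calling the primary analysis invalid.

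**What to change.** - In SAP 7.10.1 and 7.10.1.1, state the outcome window in terms consistent with Protocol 13.2.
- In the same place, say how two groups are coded: ward events in gaps between monitoring periods, and events in MFAS patients who never started monitoring. Requiring onset inside a monitoring period follows Protocol 13.2 but would count a ward event in a gap as no RD, which sits uneasily with an objective framed around opioid therapy on the ward. The choice should be explicit.
- In SAP 9.4 and the CEC Charter, let only an RD inside the stated window stop review of a patient's Episode-Files.
- Keep adjudicating out-of-window clinical events and report them separately, as is already planned for endpoint #2.
- Send to the CEC any unreviewed Episode-Files of patients whose only confirmed RD was out of window.

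The cost is wording in two documents, a few extra file reviews, and possibly slightly fewer RD cases for the model.
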